**Project Title: Testing Self-Control as a Behavior Change Mechanism to
Increase Physical Activity**

NCT04522141

Study Protocol and Statistical Analysis

Upload Date: 03/11/2022
Document Date: 09/09/2020

The overall goal of the study is to test the efficacy of a smartphone-based self-control intervention to increase physical activity among sedentary adults who are at risk for poor health. The specific aims of the study are threefold: The first aim is to test the efficacy of a self-control intervention to increase physical activity by comparing two experimental conditions (i.e., self-control treatment group vs. control group). It is expected that those who receive the self-control intervention, will show greater increases in physical activity compared to people in the control group, who do not receive the self-control intervention. Moreover, it is expected that effects in the self-control treatment group will last longer compared to any changes in the control group. The second aim is to compare changes in self-control between the self-control group and the control group. It is expected that people in the self-control group will show greater changes in self-control compared to people in the control group. The third aim is to examine self-control as a behavior change mechanism for physical activity. It is expected that those who show greater increases in self-control will also show greater increases in physical activity. Self-control is expected to mediate the relationship between condition and physical activity.

Methods

This study has been approved by the University's Institutional Review Board at Brandeis University (#20100R) and the protocol has been registered at ClinicalTrials.gov (#NCT04522141). Informed consent will be obtained from each participant. Ethical issues will be continuously considered. There is a data and safety monitoring plan and a safety officer is assigned to the study. Any adverse events will be recorded and reported.

Participants

A total of 70 sedentary middle-aged adults, who are at risk for poor health, will be enrolled. Participants will be recruited from across the US by posting flyers on public boards in libraries, churches, shopping centers/malls, or grocery stores. Moreover, we will post advertisements online on Social Media, on Craigslist, and on findparticipants.com. As

reimbursement, participants will receive a Fitbit Charge 4 step counter, which they can keep after the end of the study. In addition, as an added incentive, all participants will receive \$25 for completing all aspects of the study.

Participants will be included if they indicate they want to become more physically active, are between 35 and 65 years, are fluent in English, fit enough to walk for at least 20 minutes at a time, and own a smartphone (Android or iPhone) with a data plan. Participants will be excluded if they have experienced a fall or heart problem/condition in the last 6 months, are currently participating in an exercise program to increase physical activity or currently using a Smartwatch (e.g., Fitbit, Garmin, Apple Watch etc.) to track their physical activity, already exercise at least 3 times per week and for more than 30 minutes at a time, and/or if a doctor has advised them to not walk due to health conditions.

Study Design and Procedure

The current study uses a two-armed randomized controlled trial design with assessments at pretest (baseline), at the end of weeks 1-7, posttest (week 8), and follow-up (week 12). Participants will be randomly assigned into two experimental conditions to ensure that the two conditions are fully randomized with respect to participants' baseline characteristics (allocation concealment). Thirty-five participants are randomized into each condition. Also, participants are blinded in terms of their experimental condition.

Recruitment flyers and advertisements specify: "Do you want to be more active, but find yourself making excuses to avoid exercise?" Flyers and advertisements also include a web link for interested participants. This web link will provide detailed information about the study and interested participants will be asked to fill out a screening questionnaire to check for all inclusion and exclusion criteria. If they are eligible for the study, they will be asked to provide their phone number and home postal address so we can send them the study materials. After that, participants will be randomly assigned into one of the two experimental conditions: The self-control treatment group or the control group. A research assistant will call all eligible

participants to receive their informed consent by phone, to help them installing the MindHike smartphone application on their own smartphone, and to answer any questions. Once informed consent is given, we will ship participants a Fitbit Charge 4 step counter, instruction materials, a face mask, and a stylus pen to their home postal address.

Both the self-control treatment group and the control group will use the MindHike smartphone application and will use a Fitbit. The control group will receive a more basic version of the MindHike app which only sends them daily reminders to sync their step data, charge their Fitbit and asks them for their daily mood. The self-control treatment group will receive the version of the MindHike app which delivers the self-control intervention.

MindHike is a smartphone application which can prompt participants with messages using a chatbot system. The app is pre-packaged, which means that the app will deliver the same dialogues automatically to all participant in each condition. There is no bi-directional communication, but participants click on predesignated responses to advance the dialogue.

On the first study day, all participants will fill in a pretest questionnaire. The MindHike application will send a web link that forwards participants to this online questionnaire. All participants will be asked to wear their Fitbit every day during the entire study from when they wake up to when they go to bed. During the first study week, participants are only asked to wear the Fitbit to document the number of steps taken to establish an objective measurement of steps before the intervention. All participants will be contacted by the MindHike app twice each day for eight weeks. The first message is a push notification which reminds all participants to wear their Fitbit so they can get used to it. The timing of this Fitbit is set to 7 a.m. by default but participants can change the time if they get up earlier or later in the morning. The second daily push notification asks participants to open the MindHike app and to read through a short daily pre-packaged chat in the app. Again, the time for this second push notification can be customized by each participant. During the first week, this pre-packaged chat will only remind participants of both groups to sync their step

data with the Fitbit app and to charge their Fitbit. After this baseline week, the study will last for 7 more weeks, and participants will still receive a push notification reminder to wear their Fitbit at customized times in the morning. Across the study, participants will also fill in weekly assessments of self-control at the end of each week. After the seven weeks, participants will fill in a posttest assessment. The MindHike application will send them the web link to the online posttest. After the posttest, participants do not use the MindHike application anymore, but we will contact them via e-mail for a last online follow-up assessment four weeks later.

Control Group

After the first study week (baseline week), all participants will receive a push notification which reminds them to open the app at least once per day. If they open the app, participants will receive a pre-packaged chat. These daily pre-packaged chats will differ between the two treatment groups. Although both groups will use the MindHike application at the same frequency, the daily pre-packaged chat for the control group will only include a reminder to sync their step data, charge their Fitbit and ask them for their daily mood.

Self-Control Treatment Group

The daily pre-packaged chat for the self-control treatment group will include a short coaching session to deliver the components of the self-control intervention. For this study, the intervention was adapted to specifically target self-control in the domain of physical activity.

As part of the intervention, participants of the self-control treatment group set themselves a specific physical activity goal such as “Each evening after dinner, I will go for a 20-minute walk”. The self-control intervention will teach participants different strategies on how to achieve their personal goal. In general, participants learn how to change their behaviors in ways that potentiate their desirable impulses or weaken their undesirable ones. The intervention is based on the process model of self-control (Duckworth, Gendler, & Gross, 2016). This theoretical model will be used to describe the timeline of the development of

impulses to participants. The goal of the self-control intervention is to target each stage of this theoretical model (i.e., (1) how to proactively select situations, (2) how to proactively change certain situations, (3) how to shift attention in a given situation, (4) how to change appraisal of a given situation, and (5) how to change behaviors in a given situation). Interventional components include specific behavioral tasks (e.g., If-then plans; Gollwitzer, 1999), self-reflection tasks, and short film clips for psychoeducational purposes. Every week of the 7-week intervention, participants focus on one of the five stages of the self-control process model, while the first week is an introductory week on self-control and the last week serves to practice all learned strategies in everyday life. Each stage of the five stages of the self-control process model will be introduced with a short video clip.

Statistical Analyses

Sample size and power considerations. We conducted a power analysis for repeated measures and between-group effects based on the between-group effect size found in a previous physical activity intervention study (Robinson et al., 2019). The power analysis with an α error level of 0.05, a statistical power ($1-\beta$) of 0.80, a correlation of 0.50 between the pretest, posttest, and follow-up assessment, and a Cohen's $f = .30$ suggests a sample size of at least $N = 62$. As we learned from previous similar smartphone-based physical activity studies, about 10% of participants who sign up for the study discontinue their participation. As such, we will recruit a total of 70 middle-aged adults.

Data analyses. SPSS and R will be used to analyze differential effects between the two conditions. Multilevel models and the lme4 package in R will be used to examine group differences in change and maintenance of effects over time in objectively measured daily steps, self-reported physical activity, self-control as well as differential change over time in secondary outcomes such as Big Five personality traits, exercise self-efficacy, satisfaction with life, sense of control, and cognitive performance.

Another focus will be to examine self-control as a mechanism of behavior change. We will use multilevel models to examine whether individuals who change more in self-control also increase more in their physical activity. Moreover, we will use PROCESS in SPSS and multilevel mediation analyses in R to test whether self-control mediates the relationship between condition and physical activity.

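### Is the activity screen too loose for a sample that the protocol calls sedentary?

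*Combined protocol and SAP*

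**What the plan says.** The opening paragraph gives the overall goal as testing whether the app can "increase physical activity among sedentary adults who are at risk for poor health". The Participants section repeats the description: "A total of 70 sedentary middle-aged adults, who are at risk for poor health, will be enrolled". Neither place defines sedentary or says what marks a person as being at health risk.

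The criteria follow in the same section. One exclusion sets an activity level: people who "already exercise at least 3 times per week and for more than 30 minutes at a time". Two further exclusions concern activity without setting a level. They remove people who "are currently participating in an exercise program to increase physical activity or currently using a Smartwatch" for tracking. On the inclusion side, "Participants will be included if they indicate they want to become more physically active", along with age 35 to 65 and a minimum walking ability.

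Under Study Design and Procedure, the recruitment text asks: "Do you want to be more active, but find yourself making excuses to avoid exercise". Eligibility is checked by a screening questionnaire. "After that, participants will be randomly assigned into one of the two experimental conditions", and the Fitbit is shipped only after consent. The first study week is reserved for wearing the Fitbit "to establish an objective measurement of steps before the intervention". The Statistical Analyses section plans multilevel models of change and maintenance in daily steps. It does not list a descriptive baseline table.

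**The concern.** A reader who takes sedentary in its everyday sense expects a screen that keeps out people who exercise regularly. Because the exclusion joins frequency and duration with an and, it does less than that. It puts no ceiling on people whose sessions last 30 minutes or less, however often they exercise, and none on people who exercise once or twice a week, however long the session. It also counts only exercise, so people who are active through work or transport pass.

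What would be at stake is the reach of the conclusion. If many enrolled people were already fairly active, a claim of efficacy in sedentary adults would cover more than the trial had studied. Since the analysis section names no baseline description of steps, a reader might have no figure with which to judge this.

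**Working it through.** **1. Does the plan's own figure depend on this?** The inputs, from Statistical Analyses, are alpha 0.05, power 0.80, f = 0.30, three assessments (m = 3) and correlation 0.50. Under Study Design and Procedure there are two equal arms. For the between-group F test in a repeated-measures design:

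lambda = f² x N x m / (1 + (m - 1) x rho), with df 1 and N - 2.

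- N = 62: lambda = 0.09 x 62 x 3 / (1 + 2 x 0.50) = 16.74 / 2 = 8.37; power 0.812.
- N = 60: lambda = 0.09 x 60 x 3 / 2 = 8.10; power 0.799.

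So 62 is the smallest even total that reaches 0.80, as the plan says. With 10% dropout, 62 / 0.9 = 68.9, or 69, and 70 are recruited (70 x 0.9 = 63 completers). No activity threshold and no share of sedentary participants enters the calculation.

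**2. What does the cut-off let through?** Take weekly minutes = sessions x minutes per session, in whole minutes. A person is excluded if sessions are 3 or more and minutes exceed 30.

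| Pattern | Min/week | Cut-off | Ratio to 93 |
|---|---|---|---|
| 3 x 31 | 93 | excluded (least possible) | 1 |
| 2 x 47 | 94 | passes | 1.01 |
| 5 x 19 | 95 | passes | 1.02 |
| 4 x 24 | 96 | passes | 1.03 |
| 4 x 30 | 120 | passes | 1.29 |
| 7 x 30 | 210 | passes | 2.26 |
| 2 x 120 | 240 | passes | 2.58 |

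The first three contrasts with 93 amount to 1 to 3 minutes of self-reported exercise and carry no weight. The patterns that matter are daily sessions at the 30-minute limit and very long sessions once or twice a week.

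**3. Is that a contradiction?** Only if total weekly minutes is the intended scale. The criterion is written in frequency and session length, which is a screen for an established exercise habit. Any rule that requires two thresholds together will rank some people differently from their product, so the ordering in the table does not by itself show an error.

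**4. Do the other criteria matter?** They set no level, but they work in the same direction. Someone exercising 30 minutes every day fits poorly with recruitment text about excuses to avoid exercise. That person must also be outside any exercise programme, not be tracking activity with a smartwatch, and want to be more active.

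**5. Would a different rule be better?** Every excluded person has a total above 3 x 30 = 90, so a rule excluding totals above 90 minutes a week would keep all current exclusions. It would newly exclude 7 x 13 = 91 and still admit 2 x 40 = 80. It replaces one working definition with another, and the documents give no basis for preferring it. Changing rules after enrolment had begun would mix two eligibility definitions.

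**6. Could baseline steps be used for screening?** No. Allocation comes before the Fitbit is shipped, so week-1 steps are measured after randomisation. They can describe the sample. During that week both arms get the same sync and charge reminders, so the figures are comparable between arms.

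**The case for a change.** The strongest case for a change is that sedentary is the population named in the efficacy goal, and so is likely to pass into the paper's conclusion. The protocol's own illustration sharpens this. Under Self-Control Treatment Group, the example of a personal goal is a 20-minute walk every evening, or 7 x 20 = 140 minutes a week. A person who already does that passes the activity cut-off, and so could enter at the illustrative target. Tidying the wording would cost a sentence, and a baseline step summary one table row.

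Part of this stands. The word is undefined, the cut-off alone would pass such a person, and the analysis section names no baseline table. But the example is one possible goal, not a threshold, and the other criteria and the recruitment text make such a person a less likely entrant. The three aims compare the two conditions and are not themselves restricted to sedentary adults. A model of change in daily steps would ordinarily estimate a starting level, and nothing in the plan suggests that baseline steps would be withheld. What is left is good reporting practice, not a fault in the design or the analysis.

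**Conclusion.** No change to the plan is needed. The reading of the criterion is correct and the arithmetic holds: the cut-off excludes 93 minutes a week and passes 210. But calling the screen looser than its label needs a definition of sedentary that the documents do not contain. Read together, the criteria under Participants serve as that definition, and the health-risk phrase most naturally describes the same people.

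The effect is confined to the description of the population. Allocation, the between-arm comparison and N = 62 stay as they are. The size of any mismatch cannot be computed, because the documents do not show how many participants would have the patterns in the table.

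This rests on analysts doing what is usual: describing the sample by the criteria applied, and showing baseline-week steps overall and by arm. Two limits belong with those figures. They are recorded after randomisation from people who know they are wearing a tracker, and without a step threshold they cannot classify anyone as sedentary.

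### Random assignment precedes the phone call that takes informed consent, and no described step keeps the arm from the caller until consent is recorded

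*Combined protocol and SAP*

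**What the plan says.** The Study Design and Procedure section of the combined protocol and SAP gives the order of events. Interested people are asked to "fill out a screening questionnaire to check for all inclusion and exclusion criteria", and those who qualify leave a phone number and postal address. Then: "After that, participants will be randomly assigned into one of the two experimental conditions". The call comes next. The sentence begins "A research assistant will call all eligible" and continues "participants to receive their informed consent by phone, to help them installing the MindHike smartphone application on their own smartphone". No consent step is described before that call. The Fitbit is shipped only after consent, and the pretest is completed on the first study day through a link sent by the app.

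Two statements bear on protection of the assignment. Randomisation is said to serve balance on "baseline characteristics (allocation concealment", with the bracketed term closing the sentence and no procedure given. The section also says that "participants are blinded in terms of their experimental condition", without mentioning research staff. The arms use different software: "The control group will receive a more basic version of the MindHike app".

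On numbers, the Participants section enrols 70 people, and Study Design and Procedure says "Thirty-five participants are randomized into each condition". The Statistical Analyses section does not say how people who decline after assignment are counted or analysed, and it defines no analysis population.

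**The concern.** Allocation concealment means that the assignment stays unknown to those who settle entry until entry is settled. Balance on baseline characteristics is what randomisation itself gives on average, so attaching the term to that aim does not supply the safeguard. Here entry is settled by consent, consent is taken by phone after assignment, and the person taking it also helps install software that differs by arm. The caller could therefore know the arm while asking for consent.

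If so, and if calls are handled differently by arm, refusal may depend on the arm. People who refuse leave nothing after the screening answers, so they cannot be analysed as assigned. The groups compared could then differ from the groups randomised in a way that no later analysis fully repairs.

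**Working it through.** **1. What each stage leaves behind.**

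| Stage, in the written order | Data held if the person stops here |
|---|---|
| Online screening and contact details | Screening answers only |
| Random assignment | Screening answers and an arm |
| Call: consent, then help with installation | If consent is refused: the same, nothing more |
| Fitbit shipped; pretest on first study day | Pretest and steps begin |

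A person who declines at the call therefore has an arm but no pretest, step or outcome value.

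**2. When this biases the comparison.** If neither the participant nor the caller knows the arm, refusal cannot depend on it, and the comparison among consenters is still a randomised one. Bias needs a caller who knows the arm and acts on it. The documents are silent on both.

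**3. The plan's sample size.** Inputs from Statistical Analyses: f = 0.30, m = 3 assessments, correlation 0.50, alpha 0.05, power 0.80, two groups. For the between-group test, lambda = f² × N × m / (1 + (m − 1) × rho) = 0.09 × 62 × 3 / 2 = 8.37, with 1 and 60 degrees of freedom. Power is 0.812 at N = 62 and 0.799 at N = 60, so N = 62 is reproduced. Dropout: 62 / 0.90 = 68.9, so 69; the plan uses 70.

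**4. Where the counting point matters.** If the 70 are counted at consent, 70 × 0.90 = 63 remain (power 0.82). If they are counted at assignment and refusals come on top of the 10% dropout, the result depends on a refusal rate that the documents do not give:

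| Assumed refusal after assignment | Remaining (rounded down) | Power |
|---|---|---|
| 5% | 70 × 0.95 × 0.90 = 59 | 0.79 |
| 10% | 70 × 0.90 × 0.90 = 56 | 0.77 |
| 20% | 70 × 0.80 × 0.90 = 50 | 0.72 |

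If refusals are already inside the 10%, nothing changes.

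**5. Illustrative size of the bias (all inputs assumed).** Motivation is standard normal, and the 3 or 4 least motivated of 35 are lost in one arm only. Simulated mean of those remaining: 0.165 SD for 3 lost (8.6%) and 0.211 SD for 4 lost (11.4%). The large-sample value phi(z)/(1 − p) at p = 0.10 is 0.195.

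The planned models examine change, so a shift in level is largely absorbed. At the plan's correlation of 0.50, the SD of change is sqrt(2 × (1 − 0.50)) = 1.0 SD. Bias in change = shift × correlation of motivation with change:

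- correlation 0: bias 0;
- correlation 0.2 (for example 0.3 with pretest and 0.5 with posttest): 0.165 × 0.2 = 0.033 to 0.211 × 0.2 = 0.042;
- loss of 15% in one arm and 5% in the other, correlation 0.2: (0.274 − 0.109) × 0.2 = 0.033.

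Bias is proportional to the correlation and cannot exceed the shift itself, 0.21 SD for this loss.

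**6. Set against precision.** The standard error of a two-arm difference in change at N = 62 is 2 / sqrt(62) = 0.254 SD. The largest illustrative value at correlation 0.2 is 0.042 / 0.254 = 0.17 standard errors, which would move a two-sided 5% error rate to about 5.3%.

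**The case against.** The strongest reply is that little room is left for selection. Eligibility is settled online, so the caller has no eligibility decision to make. Detailed study information is given on the website before assignment. Everyone eligible is called. Participants are blinded, so their own preference for an arm should not drive refusal. The app is automated, and the first-week chat is identical in both groups. The only remaining route is the caller's conduct. The illustration is also severe for its loss rate: it removes exactly the least motivated, from one arm only. All of this stands, and it is why the likely effect is small. It does not close the remaining route, and it does not tell the analyst whom to include.

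A second reply is that the section may be loosely worded and consent may in practice have come first. If so, a one-sentence correction settles the matter.

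Third, a reader might infer that 70 enrolled and 35 randomised per arm contradict each other unless nobody refuses. The documents do not support that. The figures conflict only if one is counted at consent and the other at assignment. If both are counted at the same point they agree whatever the number of refusals, and neither counting point is stated. This is an ambiguity, not an inconsistency.

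Fourth, the missing analysis population would be a gap even with consent taken first. That is right, and it adds nothing to the weight of this point. It is mentioned because the order of steps determines who can be in that population.

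**Conclusion.** The point holds as a weakness in a stated procedure that is cheap to remove. As written, assignment precedes consent, no described step hides the arm from the person taking consent, people who decline after assignment cannot be analysed as assigned, and the counting point for the 70 is open.

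Two stronger conclusions are tempting and not supported. A reader might infer that the caller knew the arm, or that selection took place; the documents say neither. A reader might also infer that the trial is underpowered. The stated N = 62 reproduces, and both N = 62 and N = 70 are unaffected if participants are counted at consent. Power falls only if counting is at assignment and refusals come on top of the 10% dropout.

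The size of any bias is unknown and probably small. It is zero if the caller is unaware of the arm or does not act on it, or if the trait behind refusal is unrelated to change. It is about 0.03 to 0.04 SD under the assumed one-sided loss of 3 or 4 of 35 and a correlation of 0.2, and larger in proportion if that correlation is higher. Confidence is medium, because the deciding fact, what the caller knew, is not documented.

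**What to change.** **If enrolment is still to come or under way:**

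- Within the existing call, obtain and record consent first, then generate or reveal the allocation, then install the assigned app version. Set the version centrally if possible, so that the caller need not see it while helping with installation and answering questions.
- Replace the bracketed mention of allocation concealment with a description of this procedure.
- Count the 35 per arm from consented participants.
- Analyse all consented, randomised participants in their assigned arm, and report by arm those who consent but give no pretest or step data.

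**If enrolment already followed the written order** (the document is dated 09/09/2020 and was uploaded 03/11/2022, so it may have):

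- Report by arm the number assigned but not consented, and state who knew the arm at the call.
- State where the 70 were counted, and define the analysis population accordingly.
- Compare decliners with participants on screening answers only if use of those data is permitted, since these people did not consent. Expect little from it: the questionnaire checks eligibility, so the answers vary little among people who are all eligible.

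The cost is low. The first route changes the order of steps within one call and needs a short amendment, with no added calls, measurements or participants. The second needs a flow-diagram row by arm and a few sentences.

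### Aim 1 has two unranked activity measures, each examined for change and maintenance, with no primary test or multiplicity rule, while the sample size assumes one test at 0.05

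*Combined protocol and SAP*

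**What the plan says.** The opening statement of aims expects that the intervention group "will show greater increases in physical activity compared to people in the control group". It adds a second expectation, that effects will outlast any change in the control group. No activity measure, time point or contrast is named.

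The Data analyses paragraph will apply multilevel models to "group differences in change and maintenance of effects over time in objectively measured daily steps, self-reported physical activity, self-control as well as" to change in outcomes it calls secondary (personality, exercise self-efficacy, life satisfaction, sense of control, cognition). Neither activity measure is on that secondary list, and neither is ranked above the other.

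The sample size paragraph is "based on the between-group effect size found in a previous physical activity intervention study". It uses Cohen's f = 0.30, power 0.80 and "a correlation of 0.50 between the pretest, posttest, and follow-up assessment". "The power analysis with an α error level of 0.05" is the only mention of a significance level. The result "suggests a sample size of at least" 62, and 70 will be recruited.

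Study Design and Procedure places the posttest at week 8 and the follow-up at week 12. It also states that participants are blinded to condition.

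**The concern.** The plan does not say which result would establish that the intervention increases activity. Two measures and two questions (change, maintenance) give up to four comparisons bearing on Aim 1, and an analyst could decide which one counts after seeing the data. The stated error level and power belong to a single test that the analysis section does not identify.

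The two measures can also disagree. One comes from a device and the other from the participant. The treatment arm sets activity goals and receives daily coaching, while the control arm receives sync and charging reminders and a mood question. A favourable self-report with no difference in steps could then be reported as efficacy, and nothing in the plan rules that out.

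**Working it through.** **1. The plan's own figure.** Inputs from the sample size paragraph: f = 0.30, alpha = 0.05, power 0.80, correlation ρ = 0.50, m = 3 assessments, two groups. For the between-group test in a repeated-measures ANOVA,

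λ = N f² m / (1 + (m − 1)ρ), with 1 and N − 2 degrees of freedom.

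At N = 62, λ = 62 × 0.09 × 3 / 2 = 8.37, the critical F is 4.00 and power is 0.812. At N = 60 power is 0.799, so 62 is the smallest even N that reaches 0.80. The stated figure reproduces. The group-by-time version gives N = 20 and the two-assessment between-group version gives 68. The plan is therefore powered for one overall group comparison averaged over three assessments including pretest, which is neither the change nor the maintenance question.

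**2. Familywise error, independent tests.** Each test is taken as two-sided 0.05. This is an assumption, since no level or sidedness is given for the Aim 1 tests.

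- Any rejection: 1 − 0.95² = 9.75% for two tests; 1 − 0.95⁴ = 18.5% for four.
- Rejections favouring treatment only: 1 − 0.975² = 4.9%; 1 − 0.975⁴ = 9.6%.

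**3. Familywise error, correlated tests.** Two contrasts on one measure have a correlation implied by ρ = 0.50 if it holds for every pair of assessments. If both are taken from baseline, it is (1 − ρ) / (2(1 − ρ)) = 0.5. If maintenance is posttest to follow-up, it is −0.5. The correlation between steps and self-report is not in the documents, so a range is shown. Results are from 2 million multivariate-normal draws; the independent rows use the formulas in step 2.

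| Tests | Assumed correlations | Either direction | Favouring treatment |
|---|---|---|---|
| 1 | – | 5.0% | 2.5% |
| 2 (one per measure) | independent | 9.75% | 4.9% |
| 2 | measures 0.3 | 9.5% | 4.8% |
| 2 | measures 0.5 | 9.1% | 4.5% |
| 2 | measures 0.8 | 7.8% | 3.9% |
| 4 | independent | 18.5% | 9.6% |
| 4 | contrasts −0.5, measures 0 | 17.3% | 9.8% |
| 4 | contrasts 0.5, measures 0.3 | 16.9% | 8.5% |
| 4 | contrasts 0.5, measures 0.5 | 16.2% | 8.1% |
| 4 | all 0.7 | 13.0% | 6.5% |
| 4 | all 0.8 | 11.4% | 5.7% |

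**4. Correcting afterwards.** With the formula in step 1 at N = 62, Bonferroni gives per-test power of 0.72 at 0.025 (two tests) and 0.63 at 0.0125 (four tests), against 0.81 at 0.05.

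**5. Naming one week-8 test.** With two equal groups, d = 2f = 0.60, assumed to apply at week 8, and ρ = 0.50 is assumed to hold between baseline and week 8. The noncentrality is d / √(v × 2/n), with n per arm and v the variance factor.

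- Baseline-adjusted, v = 1 − ρ² = 0.75: at N = 62, 0.60 / √(0.75 × 2/31) = 2.73, power 0.77; at N = 70, 2.90, power 0.82. The plan's 10% loss leaves 70 × 0.9 = 63 participants, where power is again about 0.77.
- Change score, v = 2(1 − ρ) = 1: power 0.64 at N = 62 and 0.70 at N = 70.

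**The case against.** The strongest reply is that the inflated error depends on rules nobody wrote. The plan does not count its tests, does not say that any one significant result proves efficacy, and does not say the tests will go uncorrected; 0.05 is only a power input. One group-by-time test per measure is a natural reading and gives two tests. Maintenance presupposes an effect to maintain, so if it is read only after a change effect it adds no route to a false claim. All of this stands, and it is why a range is given. It does not remove the gap: the text states none of these restrictions, and two tests already raise the either-direction error to about 8-10%.

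A reader might infer stronger things that the documents do not support:

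- **That a false efficacy claim has a 13-18% chance.** Figures of that size count rejections in either direction and assume four tests. Aim 1 is directional, and the matching figures are about 6-10% against 2.5%.
- **That self-control adds further routes to a false Aim 1 claim.** It belongs to Aim 2, a separate hypothesis; a false positive there is not a claim that activity rose.
- **That participants know their arm.** The plan says they are blinded, and both arms use the app equally often. App content visibly differs, so self-report may diverge from steps, but knowledge of assignment is not established.
- **That naming a primary test is free.** A week-8 contrast has less power than the averaged test behind N = 62.

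**Conclusion.** The point holds as a gap in the definition of the efficacy claim. Aim 1 rests on two unranked measures, with no deciding test and no multiplicity rule, and the power statement describes a test that the analysis section does not contain.

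The size is conditional on an any-significant-result rule and two-sided 0.05 tests:

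- either direction: about 8-10% with two tests and 11-18.5% with four, against 5%;
- favouring treatment: about 4-5% and 6-10%, against 2.5%.

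The correlation between the two measures is assumed throughout. The arithmetic behind N = 62 is not in dispute. This should be corrected: the data stay interpretable, but what would count as efficacy is undefined until a deciding test is named.

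**What to change.** In Data analyses, preferably before outcomes are compared by arm:

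- Name one primary test for Aim 1: the between-arm difference in mean daily Fitbit steps at week 8, adjusted for the baseline week, two-sided 0.05. Steps suit this role because the first study week exists to give an objective pre-intervention step count.
- Make maintenance of steps a key secondary question, interpreted only if the primary test is significant. State whether Fitbit steps are collected up to week 12. The plan asks for wear throughout the study, but after posttest it describes only an e-mailed online assessment.
- Report self-reported activity as supportive, with confidence intervals and no efficacy claim of its own.
- Keep self-control as the separate Aim 2 hypothesis, not conditional on week-12 steps; otherwise fading activity would block a main aim.
- Restate power for the named contrast. Under the assumptions in the working it is about 0.77 at N = 62 and 0.82 at N = 70, against 0.81 at N = 62 for the averaged test.

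The cost is a few sentences and a revised power statement. The primary test needs no data beyond those planned. The downsides are that self-report alone can no longer support efficacy, and that the 0.80 target is narrowly missed if only 62 or 63 participants are evaluable.
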